### 3.2.2 Release Version 2 (Phase II)

Release version 2 expands on version 1 with the addition of new features and content based on product feedback from participants in a recently completed feasibility study of a Spark prototype. Minor modifications may also be made based on feedback from participants who received version 1.

Features/content to be added:

- Interactive psychoeducation focusing on the TRAP (trigger/response/avoidance pattern) and TRAC (trigger/response/alternative coping) model of depression and how it relates to behavior activation.
- A mood tracking feature that enables users to practice recognizing the relationship between their mood and their behavior. The feature will accomplish this by prompting users to log activities that they have done and how those activities made them feel. Users will also learn the concept of 'up activities' (those that improve their mood) and 'down activities' (those that worsen their mood) and will apply this concept by categorizing their logged activities as either 'up' or 'down'.
- The activity scheduling feature from version 1 will be enhanced by enabling users to 'favorite' their 'up' activities, and subsequently schedule favorited activities as behavioral activations. For example, if a user categorized 'riding my bike' an up activity, then that activity can be favorited and easily scheduled as a behavioral activation.
- Two new tabs in the user interface. A highlights tab that enables users to view summaries of their mood logs, up activities, favorites, and completed activities and associated values. A 'My Logs' tab has also been added that enables users to browse their mood-activity logs and behavioral activations by date.
- 

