#### **Program Flow:**

- Lesson 1: Understanding behavior
  - Introduction to program
  - The brain and behavior
  - Studying the brain
  - The teenage brain
- Lesson 2: Exploring the brain
  - Depression in the brain
  - Brain structure
  - Brain function
  - Depression in teens
- Lesson 3: Mastering Messengers
  - Messages in the brains
  - Neurotransmitters
  - Messengers in depression
  - Teens and transmitters
- Lesson 4: Riding the Wave
  - Hormones and behavior
  - Hormones in depression
  - Puberty & the brain
  - Puberty & depression
- Lesson 5: People & personality
  - What are genes?
  - Personality
  - Big 5
  - Big 5 interactive task
  - Genes & depression

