###### Phase II

- Remission rates based on PHQ-8 < 10
- Between-group treatment-related differences in participant-rated anxiety symptoms and global functioning as measured by GAD-7 and PROMIS Pediatric Global Health Scale
- Between-group treatment-related differences in parent-reported depressive symptoms and global functioning as measured by MFQ, and PROMIS Parent Proxy Global Health Scale
- Average treatment-related usability (SUS) and engagement (UES-SF) ratings
- Between-group treatment-related differences in clinical concern rates and serious clinical concerns
- Between-group treatment-related differences in program adherence and engagement based on behavioral and mobile app analytics
- 

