imputation methods may also be used and a specific approach for imputation will be selected based on key attributes of the obtained data, including % missing and whether data are missing at random^109. Sensitivity analyses will be conducted to determine if data are missing at random. In these analyses, allowing for random intercepts and slopes, the change (slope) will be the key dependent variable and the randomization status will be the key independent variable. The results of these analyses can be easily converted to group or treatment differences at post assessments. In our mixed effects modeling, all variables will be analyzed as continuous with the exception of clinical concerns (occurrence/non-occurrence), which will be treated as a repeatedly measured binary outcome.

As an exploratory investigation, multiple variables will be investigated as possible moderators of treatment effects on depressive symptoms (PHQ-8). For example, we may evaluate medication status, symptom severity, age, sex, COVID19 specific factors, and aspects of program engagement (e.g., time to complete program, duration of use) as potential moderators. For this investigation, we will employ the MacArthur framework for moderator analysis, following the eligibility and analytical criteria for determining moderators. To maximize power, moderator analyses will also be conducted using mixed effects modeling.

Exploratory analyses using mixed effects modeling will also be conducted to evaluate whether successive program updates (between versions 2 and 3 of Limbix Spark) result in statistically significant differences on primary and secondary outcome measures, including depressive symptoms, global functioning, and treatment adherence, usability, and engagement.

Content analysis of post-study interviews will be conducted. Data will be codified to identify themes with an emphasis on engagement, usability, comprehension, therapeutic alliance, and overall impact of treatment. Key insights will be drawn from themes and contextualized with quantitative user session data.

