Lastly, we will assess treatment adherence by evaluating treatment-related differences in rates of program completion and daily mobile app usage using independent samples (between treatment and control groups) or paired (within the educational control group) t-tests. We will also assess treatment-related differences in self-reported usability and engagement using the SUS and UES scales descriptively by comparing means and variability between groups and within group (control group only)

Statistical analyses for the primary outcome variable and between group differences in rates of clinical concerns rates will be conducted when N=60 (~30/grp) and N=120 (~60/grp) participants have completed Phase II. If no statistical differences are detected in the primary outcome variable, possible moderators of treatment status on the primary outcome may be evaluated, including age, concurrent treatment, and PHQ-8 score at baseline. Results of the interim analyses may be used to adjust recruitment targets for the remainder of the trial.

An effect size will be calculated for the primary outcome and may be used to determine sample size for a Phase III trial.

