#### **4.5 Data Monitoring**

This is a low risk research study.

A clinical concern is defined here as any negative experience or symptom reported by participant or parent in the Participant Symptom Check Questionnaire, in freeform text, spontaneously reported, or clinically significant deterioration of symptoms, whether or not thought to be associated with participation in the study.

Clinical concerns will be categorized as follows:

0- Not a clinical concern: Research team determined that triggering event was not a clinical concern

1- Mild clinical concern: Research team determined that triggering event doesn't require clinician input and will continue to monitor participant's responses

2- Moderate clinical concern: Research team determined that triggering event requires clinician input. Clinician determined that research team should continue to monitor participant's responses but that no follow-up was needed.

3- Elevated clinical concern: Research team determined that triggering event requires clinician input. Clinician determined follow-up was indicated and confirmed participant safety (participant did not endorse intent to self harm) via email or phone communication with participant or their parent/guardian or their provider.

4- Significant clinical concern: Research team determined that triggering event requires clinician input. Clinician determined that follow-up was indicated and after follow-up with participant, parent/guardian, or provider determined that participant should be withdrawn from study (e.g. due to suicide attempt, self-harm or self-harm attempt, suicidal ideation with intent, reported hospitalization for self-harm or suicide attempt while enrolled in study).

All adverse device effects and complaints will be recorded (whether anticipated or unanticipated). The project PI and study clinician will determine whether it is in the participant's best interest to remain in the study after any clinical concern.

Anticipated serious clinical concerns, given the study population, include depressive symptoms as defined in the DSM-V, suicidal ideation, active self-harm, clinically significant deterioration in depressive symptoms, suicide attempts, and suicide.

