### **7.3 Protection Against Risk**

To minimize psychological risks, participants will be instructed that they can choose not to answer any question in any assessment and can discontinue their participation at any time. As the mobile app progresses in a linear fashion, questions in the mobile program must be answered to progress to the next task. During consent, participants will be informed that if they do not wish to answer a question in the mobile app they may discontinue their participation at any time. Patient responses to assessments completed weekly will be monitored as well as free response answers to questions delivered via the mobile app. This will enable detection of deterioration in clinical status. If such deterioration occurs, research staff will immediately contact the PI/study clinician. Participation will be terminated if clinical evidence indicates that continuing would not be in the best interest of the subject as determined by study PI in consultation with a study clinician. Weekly symptom reporting will also help the research team to identify any psychological or physical health consequences of study participation and, in consultation with study clinicians, determine the best way to mitigate further risks to participant health.

To minimize risks to privacy and/or confidentiality, only personnel with training in protecting private information about human subjects will have access to study data. Special care will be taken to prevent unauthorized access to data files.

Computers on which data files will be accessed will have password-protected access. All study participants will be assigned code numbers on entry to the study and all subsequent data processing will be completed by reference to these numbers. Special care will be taken to prevent unauthorized access to the data file connecting participant identity to subject numbers.

All publications or reports of data will be anonymous in relation to subject identification. Protected health information will be disclosed to other professionals treating the patient only upon written authorization of the patient. PIs will retain responsibility for ensuring that files are maintained in a secure manner during and after study.

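### The between-arm comparison of clinical concerns pools in-app free text with sources common to both arms, so equal true rates could be recorded as unequal

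*Combined protocol and SAP*

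**What the plan says.** **What counts.** Section 4.5 (Data Monitoring) defines a clinical concern as any negative experience or symptom reported in the Participant Symptom Check, or arising "in freeform text, spontaneously reported, or clinically significant deterioration of symptoms". Section 4.5.1 has coordinators raise concerns found in free text, correspondence, interviews, weekly PHQ scores and the symptom check. Section 7.3 says that weekly assessments are monitored "as well as free response answers to questions delivered via the mobile app".

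**How it is compared.** The Phase II secondary outcomes in section 4.2 include "Between-group treatment-related differences in clinical concern rates and serious clinical concerns". Section 4.4 (Phase II) models "clinical concerns (occurrence/non-occurrence), which will be treated as a repeatedly measured binary outcome". It also says that analyses of the primary outcome and of "between group differences in rates of clinical concerns rates will be conducted when N=60 (~30/grp) and N=120 (~60/grp) participants have completed Phase II". No analysis by reporting source is described.

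**What each arm does in the app.** In the version 1 program flow (section 3.2.1), Spark users schedule activities and reflect on them. Version 2 builds on this by "prompting users to log activities that they have done and how those activities made them feel" (section 3.2.2). Version 3 adds guided problem-solving, mindfulness exercises and a personal relapse plan (section 3.2.3). The Phase II control (section 3.3.2) is five lessons on the neurobiology of depression. The only listed item that is plainly interactive is the "Big 5 interactive task" in Lesson 5.

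**What is common to both arms.** Section 3.1 gives all participants a weekly in-app PHQ-8 and concerns questionnaire. Guardians of participants under 18 get a weekly symptom check.

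**The concern.** A between-arm comparison of event rates is fair only if an event has the same chance of being recorded in each arm. Here one recording route, text typed in the app and read by staff, depends on how much the assigned program asks the user to enter. That is a feature of the intervention, not of the participant's condition. If Spark prompts more entries, the same underlying distress gets more chances to be seen on Spark.

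The comparison is a named secondary outcome and one of two quantities analysed at the interim looks. An excess on Spark could be a reporting artefact. A null result could hide a true reduction. Once the data are unblinded, the sponsor could not credibly argue either case unless source had been recorded and its use prespecified.

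**Working it through.** **Plan's own figure.** The documents size nothing for clinical concerns. The only sizing figure, 175 in section 2.1, is for the PHQ-8. It reproduces (64 per arm by the exact t calculation, 128 / 0.73 = 175.3) but does not bear on this point.

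**Direction, from the text.**

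| Feature | Spark in Phase II | Control in Phase II |
|---|---|---|
| Weekly PHQ-8 and participant symptom check | yes | yes |
| Guardian symptom check (under 18) | yes | yes |
| Mood and activity logs | yes (3.2.2) | none listed |
| Reflection on completed activities | yes (3.2.1, carried forward) | none listed |
| Problem-solving exercise, relapse plan | yes, version 3 (3.2.3) | none listed |
| Interactive task | several | one listed (3.3.2) |
| Must complete tasks to progress | stated (3.1, 3.2) | not stated |

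Section 3.3.2 matches the control on duration, amount of content, modality and interface. It does not mention the amount of user entry. The text therefore supports more occasions for entry on Spark. It does not say how many more.

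**Size, on assumed inputs.** None of these rates is in the documents.
- p = proportion with a concern from common sources over 5 weeks, the same in both arms: 20–50%
- q = proportion of the remainder flagged by free text alone: 5–25% on Spark, 0–5% on control
- n = 60 per arm (second look in section 4.4); two-sided alpha 0.05 (section 4.4)

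Recorded rate in an arm: r = 1 − (1 − p)(1 − q).

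With d the difference in recorded rates and r̄ their mean:
- se0 = √(2 r̄(1 − r̄)/n)
- se1 = √([rS(1 − rS) + rC(1 − rC)]/n)
- P(significant) = Φ((d − 1.96 se0)/se1) + Φ((−d − 1.96 se0)/se1)

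Upper end, p = 0.20, q = 0.25 against 0:
- rS = 1 − 0.80 × 0.75 = 0.40; rC = 0.20; risk ratio 2.00
- se0 = √(2 × 0.30 × 0.70/60) = 0.0837; se1 = √((0.24 + 0.16)/60) = 0.0816
- (0.20 − 1.96 × 0.0837)/0.0816 = 0.44, so P = 0.67

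Lower end, q = 0.05 in both arms: the rates are equal, so the risk ratio is 1.00 and P is about 0.05.

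| p | q Spark | q control | Recorded rates | Risk ratio | P(significant) |
|---|---|---|---|---|---|
| 0.20 | 0.05 | 0.05 | 24.0% v 24.0% | 1.00 | 5% |
| 0.30 | 0.10 | 0 | 37.0% v 30.0% | 1.23 | 13% |
| 0.30 | 0.20 | 0.02 | 44.0% v 31.4% | 1.40 | 29% |
| 0.20 | 0.25 | 0.05 | 40.0% v 24.0% | 1.67 | 47% |
| 0.20 | 0.25 | 0 | 40.0% v 20.0% | 2.00 | 67% |

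**If common sources already catch most concerns.** With p = 0.80, free text at 10% against 0 gives 82% v 80%, risk ratio 1.02 and P about 6%. At 25% against 0 it gives 85% v 80%, risk ratio 1.06 and P about 11%.

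**If only common sources are counted.** With equal true rates and equal completion of the checks, a simulation of 40,000 runs gives a false-difference probability of about 5% at each look.

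The two-proportion test simplifies the planned repeated-binary model. It shows scale and does not predict the trial's result.

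**The case against.** Five points can be made on the other side.

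1. **A reader might infer that Spark elicits far more free text. The documents do not show that.** They do not say which entries are typed. Logging an activity and classing it as up or down could use pick-lists, and the control section gives only lesson titles. This stands. More occasions for entry is as far as the text goes.

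2. **A reader might infer that severity grading adds a second bias**, because the highest grade applies when the clinician "determined that participant should be withdrawn from study". The documents do not support this for the planned model. It uses occurrence, so grades 1–4 do not enter. Only category 0, where staff judge an event not to be a concern, could affect it, and nothing indicates the direction. Section 4.2's serious concerns are not tied to the highest grade. The coordinator knows the arm (section 3.1), but the clinician's knowledge is not stated. Defining serious by the examples under that grade would also be wrong, since they omit items on section 4.5's own list of anticipated serious concerns, including suicide.

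3. **The common checks are not necessarily observed equally.** The participant checks sit inside the assigned app, and app use may differ by arm. This stands, and the fix must allow for it.

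4. **Dropping free text could remove the place where distress during Spark use first appears.** This stands against replacing the all-source comparison. It does not count against adding a second one.

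5. **No action follows automatically from a significant difference.** Stopping is a judgement (section 4.5), and the DSMB reviews all concerns quarterly (section 4.5.2). This limits the harm. It does not make the reported secondary outcome interpretable.

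**Conclusion.** The concern holds in a limited form. The plan compares a pooled count in which one source depends on the assigned app, and it has no analysis that separates that source. The likely direction is a higher recorded rate on Spark.

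The size cannot be derived from the documents. Under the assumptions shown, it runs from no effect to a doubled apparent rate, with a 5% to 67% chance of a significant difference at 60 per arm. It stays small if the weekly checks catch most concerns, which is plausible when any negative symptom counts in a depressed sample. The case for change rests on the unseparated sources and the low cost of separating them, not on any one figure in that range.

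The exploratory within-control comparison of concerns (section 4.3), which sets the control period against later Spark use, has the same weakness.

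**What to change.** - Add a source field to each clinical concern: participant Symptom Check, parent Symptom Check, PHQ-8 deterioration, in-app free text, interview, or spontaneous report.
- In section 4.4, prespecify a between-arm analysis over the first 5 weeks limited to the two Symptom Checks and PHQ-8 deterioration. Use it at the final analysis and at both interim looks.
- Report completion of those checks by arm and account for it in that analysis, for example by modelling occurrence per completed check.
- Report this beside the all-source comparison, and tabulate free-text, interview and spontaneous concerns separately by arm.
- Keep every source for individual safety monitoring and DSMB review.

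The cost is one data field and a paragraph of analysis wording. The restricted comparison will have fewer events, and differential completion of the in-app checks may leave some residual bias.

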#### **4.5.1 Study Staff Responsibilities**

Data monitoring will be conducted by the research coordinator and overseen by project PIs. In the course of data collection and monitoring, study coordinators will follow an internal safety protocol and alert a study PI or study clinician of any clinical concerns that occur during baseline or post study interview sessions, in freeform text, email/text/phone correspondence, in weekly PHQ scores, and the weekly participant symptom check.

The PIs in consultation with study clinicians will be responsible for monitoring participant safety during the study. The PIs and study clinicians will review relevant assessments, free-responses, and reports from study staff to assess whether it is appropriate for the participant to continue study participation and whether further action to ensure the safety and wellbeing of the participant is warranted. If warranted, the study clinician will reach out to the participant and parent (if under 18) to confirm safety. Because this study is low risk, the study clinicians will not be on call 24/7.

The study clinicians are licensed medical providers and have experience in the assessment of mood and anxiety symptoms, in directing the treatment of such symptoms, and in addressing possible adverse reactions during clinical trials. The study clinicians will assess the benefits and risks of the protocol on an ongoing basis and will be available to the study team for questions regarding inclusion/exclusion criteria, protocol conduct, and safety. The study clinicians will review and evaluate information relevant to the safety of this study before

the implementation of the protocol and will recommend alterations to the study design based on review of subject safety trends.

PIs will review all data collection materials on an ongoing basis for data completeness and accuracy as well as protocol adherence. Protocol deviations and violations will be reported in accordance with IRB and FDA guidelines. In this study, a protocol violation includes but is not limited to enrollment of an ineligible participant and failure to obtain informed consent. A protocol deviation includes but is not limited to minor deviations from protocol that do not impact safety or efficacy and failure to keep IRB approval up to date.

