### **Phase II**

1. Between the ages of 13 and 21
2. Self-reported symptoms of depression
3. Stable for at least two months on any treatment (including medication or psychotherapy) for a mental health disorder
4. Will be residing in the USA for the duration of the up to 12-week study
5. Under the care of a US-based primary care and/or licensed mental healthcare provider and willing and able to provide the name and contact information of the provider during consent appointment
6. English fluency and literacy of adolescent and consenting legal guardian if under 18
7. Access to a smartphone (iPhone 6s or later and running iOS 13.0 or later or running Android 4.4 KitKat or later) and regular internet access
8. Willing to provide informed e-consent/assent and have legal guardian willing to provide informed e-consent if under 18 (unless minor is legally emancipated or financially independent under relevant state laws)

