Both mobile programs (Limbix Spark and educational control) will be fully self-guided, completed by participants at home. Each program is designed to be completed over 5 weeks but users may progress through the program at their own pace. The Limbix Spark program progresses linearly, i.e., a task must be completed before a participant can progress to the next task. Content for a given week is not expected to take more than 60 minutes to complete. All participants will be prompted to complete a weekly PHQ-8 and clinical concerns questionnaire in the mobile app. Automated app notification reminders to complete these questionnaires will be sent. If users have not opened the app in 3 days, an automated app notification encouraging participants to use the app will be sent. An automated reminder notification will be sent 7 days before the end of the intervention period to remind participants that the intervention period will be ending in 7 days.

The legal guardian of participants under 18 will be emailed links to complete a parent-reported participant symptom check weekly. If they have not completed the questionnaire, they will be sent a reminder email 6 days later to remind them that the questionnaire is due the next day.

After the 5 week intervention period, participants and their legal guardian (if required) will be emailed links to complete post-intervention self-report assessments via secure web portal. Participants and their legal guardian (if required) will receive automated email reminders to complete the post-intervention assessments after 6 days if they have not completed the assessments. If participants or their legal guardian do not complete the post-intervention assessments within a week the research coordinator may reach out to participants or legal guardians via phone or email to encourage them to complete these assessments.

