In Phase II, for participants randomized to the treatment arm, if the participant does not complete the post-intervention assessments within 2 weeks from the end of the intervention period they will be considered lost to follow up. If a participant chooses to withdraw from the study at any point or the participant is deemed lost to follow up or is dropped from the study during the intervention period (5 weeks), access to the web portal and mobile app will be restricted at that time, otherwise access to the mobile app will be restricted at the end of the intervention period and access to the web portal will be restricted after post-intervention assessments have been completed or the participant is deemed lost to follow up (2 weeks after intervention period).

Participants randomized to the control arm will have two weeks to complete the post-intervention assessments. Once the post-intervention assessments have been completed or 2 weeks have passed, whichever occurs first, participants in the control arm will be granted access to the treatment condition (Limbix Spark) for 5 weeks. After access to Limbix Spark for 5 weeks, participants will have two weeks to complete another set of post-intervention assessments. If a participant chooses to withdraw from the study or the participant is deemed lost to follow up during the control app intervention period or Limbix Spark app intervention period (5 weeks

each), access to the web portal and mobile app will be restricted at that time. Otherwise, access to the mobile app will be restricted at the end of each intervention period and access to the web portal will be restricted after the second set of post-intervention assessments have been completed or the participant is deemed lost to follow up (2 weeks after Limbix Spark intervention period).

In Phase II, if participants report a change in their treatment for a mental health disorder while enrolled in the study, they may be withdrawn from the study.

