## Schedule of Assessments:

|  | Baseline | Weekly during study | Post-intervention |
|--|----------|---------------------|-------------------|
| Patient Health Questionnaire (PHQ-8)                   | X        | X                   | X                 |
| Baseline Questionnaire- Participant                    | X        |                     |                   |
| Baseline Questionnaire- Parent                         | X        |                     |                   |
| Brief Resilience Scale                                 | X        |                     |                   |
| Generalized Anxiety Disorder (GAD-7)                   | X        |                     | X                 |
| PROMIS Pediatric Global Health Scale                   | X        |                     | X                 |
| PROMIS Parent Proxy Global Health Scale                | X        |                     | X                 |
| Mood and Feelings Questionnaire (Short Parent Version) | X        |                     | X                 |
| Participant Symptom Check- Participant                 |          | X                   |                   |
| Participant Symptom Check- Parent                      |          | X                   |                   |
| Post Program Questionnaire- Participant                |          |                     | X                 |
| Post Program Questionnaire- Parent                     |          |                     | X                 |
| System Usability Scale                                 |          |                     | X                 |
| User Engagement Scale                                  |          |                     | X                 |

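### Phase II schedules no participant Symptom Check after the app locks and names no alert route for the post-intervention PHQ-8; its stated 12-week length omits the last assessment window

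*Combined protocol and SAP*

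**What the plan says.** All references are to the combined protocol and SAP.

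- **Symptom checks.** In the Schedule of Assessments, the row "Participant Symptom Check- Participant" and its parent counterpart are marked only in the weekly column. Section 3.4 puts weekly participant assessments in the app and weekly parent assessments on the web portal.
- **App lock.** Section 3.1 (Phase II) says that "access to the mobile app will be restricted at the end of the intervention period". The portal stays open until the post-intervention set is done or the participant is lost to follow-up.
- **Completion windows.** For Spark participants the limit is as follows: "if the participant does not complete the post-intervention assessments within 2 weeks from the end of the intervention period they will be considered lost" (meaning lost to follow-up). Controls have up to two weeks after the control app and then receive Spark for 5 weeks. After that, "participants will have two weeks to complete another set of post-intervention assessments".
- **What counts as a concern.** Section 4.5 includes spontaneous reports, "or clinically significant deterioration of symptoms, whether or not thought to be associated with participation in the study".
- **What staff act on.** Section 4.5.1 lists interview sessions, free text and correspondence, then concerns "in weekly PHQ scores, and the weekly participant symptom check". It adds, more generally, that the investigators and study clinicians review the assessments that are relevant. Section 7.3 describes monitoring of weekly assessments and of free responses in the app.
- **Study length.** The Phase II inclusion criterion in section 2.5 reads: "Will be residing in the USA for the duration of the up to 12-week study".

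**The concern.** There are two gaps in safety ascertainment and one inconsistent figure.

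First, the participant check is available only in the app, and nothing replaces it once the app is locked. The Post-Program Questionnaire, as described under Description of Assessments, asks about treatment changes and COVID-19, not about clinical concerns. Anything arising between the last in-app check and the post-intervention set has to be volunteered, come up in correspondence, or surface in an interview that is optional for the participant and that the coordinator need not arrange.

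Second, the PHQ-8 that defines the primary endpoint is not named as a score that must raise an alert. This matters most for controls. After their first post-intervention PHQ-8 they go on to 5 weeks of Spark, and section 4.5 requires a decision on remaining in the study after any clinical concern. No alert rule is tied to the score that could reveal one at that moment.

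Third, the length in an operative eligibility criterion is shorter than the schedule allows.

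What is at stake is complete capture of safety information in adolescents selected for depressive symptoms, and of the clinical-concern outcome in section 4.2. The primary efficacy analysis and the power are not affected.

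**Working it through.** **Inputs**

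| Input | Value | Source |
|---|---|---|
| Intervention period, either program | 5 weeks ("Each program is designed to be completed over 5 weeks") | 3.1 |
| Completion window, Spark arm | up to 2 weeks | 3.1, Phase II |
| Completion window, control arm, after each period | up to 2 weeks | 3.1, Phase II |
| Spark access for controls | 5 weeks, from completion of the first set or at 2 weeks, whichever is earlier | 3.1, Phase II |
| Stated maximum length | 12 weeks | 2.5, Phase II |

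**Step 1: study length.** The stated 12 can be reached in two ways:

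- control app + first window + Spark = 5 + 2 + 5 = 12, which leaves out the final window;
- one week per window: 5 + 1 + 5 + 1 = 12, which uses less than the time allowed.

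Neither is a maximum. With no windows, 5 + 5 = 10. With all windows in full, 5 + 2 + 5 + 2 = **14 weeks** for a control. A Spark participant has at most 5 + 2 = 7 weeks.

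**Step 2: time without a scheduled participant Symptom Check.** Each period leaves 0 to 2 weeks, because the window ends when the assessments are completed. At the upper limit:

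- Spark arm: 2 / 7 = 28.6%
- Control arm, whole participation: (2 + 2) / 14 = 4 / 14 = 28.6%
- Control arm, randomised comparison period only: 2 / (5 + 2) = 2 / 7 = 28.6%

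**Step 3: alert sources side by side.**

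| Source | Collected in | Named in 4.5.1 alert list | Named in 7.3 |
|---|---|---|---|
| Weekly PHQ-8 | app | yes | yes, as a weekly assessment |
| Weekly participant Symptom Check | app | yes | yes, as a weekly assessment |
| Free text | app and elsewhere | yes | yes, in-app responses |
| Email, text, phone | correspondence | yes | no |
| Baseline and post-study interview sessions | video call | yes | no |
| Post-intervention PHQ-8 | portal | **no** | **no** |

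The word weekly cannot simply be stretched to cover the endpoint. Section 3.4 and the Schedule of Assessments separate weekly from post-intervention assessments, by column and, for participants, by platform. Section 3.1 also ties monitoring for deterioration to the PHQ-8 in the app.

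**The case against.** The strongest reply is that other routes remain open. The post-intervention PHQ-8 is collected. The definition in section 4.5 covers spontaneous reports and deterioration without limiting either to the weekly period. Section 4.5.1 has the investigators and clinicians review relevant assessments in general, and coordinators may contact participants who have not completed the set within a week. Coordinators also follow an internal safety protocol that is not among the documents and may already cover the endpoint score. The study is classed as minimal risk. All of this stands. It limits the point to the absence of a scheduled check and of an explicit alert rule.

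A reader might infer more than the documents support:

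- **That late concerns are missed, or that endpoint deterioration prompts no review.** The routes above contradict this.
- **That all symptom checks stop with the app.** Parent checks for minors run on the portal, so the lock does not end them. For Phase II no end date is given beyond the weekly marking. Participants aged 18 to 21 have no parent check.
- **That the comparison of concern rates between arms is biased.** In the randomised period both arms have the same weekly checks, the same lock and the same maximum window. Incomplete capture is supportable; bias is not shown.
- **That the fifth weekly check is lost too.** This would require it to fall due as the app locks, and no due date is given.
- **That participants turning 18 late are overlooked.** Sections 3.1 and 8.2 tie re-consent to actual participation, not to 12 weeks.
- **That Phase I needs the same correction.** Section 2.2 treats Phase I recruitment as already observed, so changing its criterion would have little effect.

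**Conclusion.** The point holds as a modest, inexpensive improvement plus one factual correction.

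- No participant Symptom Check is scheduled between the app lock and the end of each completion window. The gap is at most 2 of 7 weeks for Spark and 4 of 14 for control (29% each). These figures assume that the full window is used; early completion shortens the gap, possibly to nothing.
- Deterioration on the post-intervention PHQ-8 is a clinical concern by the plan's own definition, but it is not named in the alert list or in the monitoring statement. Whether the internal safety protocol closes this gap cannot be judged from the documents.
- The maximum Phase II length is 14 weeks for controls, not 12. This follows from the stated period lengths without further assumption.

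**What to change.** 1. In the Schedule of Assessments, add the Symptom Check at post-intervention, delivered on the portal and covering the time since the last weekly check. For controls, use it after each of the two periods.
2. In sections 4.5.1 and 7.3, name the post-intervention PHQ-8 among the monitored sources. If the internal safety protocol already covers it, say so there. How staff respond to a given score remains for the investigators and study clinicians.
3. In the Phase II residence criterion, change the maximum length from 12 to 14 weeks so that it agrees with section 3.1.
4. State when the weekly parent checks end in Phase II.

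The cost is a few more portal questions, one more score to review, and a short protocol amendment. No extra visit is needed, because the portal is already open during these windows.
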